5.2.3. Analyses for Categorical Data

The change from Baseline in the Patient's Global Assessment of Osteoarthritis to Weeks 2, 4, 8, 12 and 16 will also be analyzed using Cochran-Mantel-Haenszel (CMH) test, stratified by the combinations of the two stratification factors. Changes by each level of improvement will be summarized, as well as any improvement (change<0), and any worsening (change>0). For this analysis imputation for missing data will used mixed BOCF/LOCF, as well as BOCF and LOCF separately. If there are too few subjects in any stratification combination group (defined as <15 subjects in any stratification factor) then an unstratified test will be performed. The mixed BOCF/LOCF analysis at Week 16 will provide a sensitivity analysis for the primary analysis of the PGA.

For any analysis using the CMH test, if there are too few subjects in any stratification combination group (defined as <15 subjects in any of the 6 combinations of stratification factors) then an unstratified test will be performed.

The change from Baseline in the NIS will be analyzed using a Cochran-Mantel-Haenszel (CMH) test for 'row mean scores differ', using change from Baseline categories as the scores in the analysis, and stratified by the combined levels of the stratification factors. Output will show number and percentage of subjects whose NIS score worsened (change>0), improved (change<0) or had no change, in addition to the mean (with standard deviation) and median change, and minimum and maximum change. This analysis will be performed for the two treatment comparisons separately, and shown by visit and worst change (largest change from baseline to any post-baseline visit), and by last change (summary statistics only).

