2.2. Study Design

The study design is summarized in the diagram below.

Figure 1. Study Design

This is a randomized, double-blind, placebo-controlled, multicenter, parallel-group, Phase 3 study of the efficacy and safety of tanezumab when administered by SC injection for 16 weeks compared to placebo in subjects with osteoarthritis of the knee or hip. Approximately 690 subjects (approximately 230 per treatment group) will be randomized to one of 3 treatment groups in a 1:1:1 ratio. Subjects will receive a total of two SC injections, separated by 8 weeks:

- *tanezumab 2.5 mg (Day 1) and tanezumab 2.5 mg (Week 8);*
- *tanezumab 2.5 mg (Day 1), and tanezumab 5 mg (Week 8);*
- *placebo to match tanezumab (Day 1) and placebo to match tanezumab (Week 8).*

The randomization will be stratified by the factors of index joint and highest Kellgren-Lawrence grade in the knee and hip joints.

This study is designed with a total (post-randomization) duration of 40 weeks and will consist of three periods: Screening (up to a maximum of 37 days), Double-blind Treatment (16 weeks, 6 in-clinic visits), and Safety Follow-up (24 weeks). The Screening Period (to begin up to 37 days prior to Randomization) includes a Washout Period (lasting a minimum of 2 days for all prohibited pain medications) if required, and an Initial Pain Assessment Period (IPAP; 7 days prior to Randomization/Baseline; minimum 3 days).

The end of treatment period is at Week 16, with the safety follow-up period up to Week 40. The primary time point for efficacy is Week 16. The period of interest for most safety results is the treatment period. Selected safety results will also be provided separately for the safety follow-up period, and some results will be provided for the combined overall study period comprising the treatment and safety follow-up periods.

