5. GENERAL METHODOLOGY AND CONVENTIONS

5.1. Hypotheses and Decision Rules

5.1.1. Statistical Hypotheses

The treatment comparisons being made in this study are tanezumab 2.5 mg and 2.5 mg then 5 mg (2.5/5 mg) versus placebo. For these treatment comparisons, the null and alternative hypotheses are shown below (note $\mu_{\text{TREATMENT}}$ relates to the mean change from Baseline for the specified treatment group). All tests will be 2-sided.

Null Hypotheses	H0: $\mu_{\text{TANEZUMAB 2.5mg}} - \mu_{\text{PLACEBO}} = 0$
	H0: $\mu_{\text{TANEZUMAB 2.5/5mg}} - \mu_{\text{PLACEBO}} = 0$
Alternative Hypotheses	H1: $\mu_{\text{TANEZUMAB 2.5mg}} - \mu_{\text{PLACEBO}} \neq 0$
	H1: $\mu_{\text{TANEZUMAB 2.5/5mg}} - \mu_{\text{PLACEBO}} \neq 0$

The hypotheses for other types of analyses (e.g. for the binary response endpoints) would be similar to those shown above.

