5.1.2. Statistical Decision Rules

The Type I error rate (α -level) used in the assessment of pair-wise treatment comparisons for the primary efficacy endpoints is 5%. The fixed sequence testing strategy of the co-primary endpoints is described below.

The assessment of significance for the tanezumab versus placebo treatment contrasts will use a step-down testing strategy within each of the co-primary efficacy endpoints. The step-down testing will first test tanezumab 2.5/5 mg versus placebo, and if statistically significant ($p \leq 0.05$) will then test tanezumab 2.5 mg versus placebo. Finally, the particular tanezumab dose group is declared as superior to placebo if the corresponding treatment contrast is significant over all three co-primary endpoints. This testing procedure will maintain the Type I error to 5% or less within each of the co-primary efficacy endpoints, and to less than 5% for all three co-primary efficacy endpoints.

The secondary endpoint of subjects with $\geq 50\%$ reduction from baseline in WOMAC Pain at Week 16 is identified as a key secondary endpoint and will be included in the testing strategy. If both tanezumab regimens are found to be statistically significantly better than placebo in the primary comparisons described above, the two comparisons of this secondary endpoint (tanezumab 2.5 mg treatment group versus placebo and tanezumab 2.5/5 mg treatment group versus placebo) will be adjusted for multiple comparisons using the Hochberg procedure and an overall significance level of 0.05.

The primary analysis will be that with the multiple imputation approach (see below for details), and thus the overall type I error is controlled for each of the two dose regimens (2.5 mg and 2.5/5 mg) since all three co-primary endpoints need to be significant for a single dose. The overall type I error of the study is also controlled given the step-down testing strategy for each of the primary endpoints and the key secondary endpoint. Control of the type I error rate accounting for multiplicity of contrasts will only apply to the three co-primary endpoints (model with the primary imputation analysis) and the key secondary endpoint.

Regardless of the outcome of the primary and key secondary analyses, the secondary endpoints will be tested. No adjustment for multiple comparisons will be made for the secondary efficacy, and for the safety endpoints. The α -level for each hypothesis test for the secondary and exploratory analyses will be 5%.

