5.2.2. Analyses for Continuous Data

The co-primary efficacy endpoints will be analyzed using an ANCOVA model, with model terms for Baseline score, Baseline diary average pain, index joint (knee or hip), highest Kellgren-Lawrence grade, and treatment group, and study site as a random effect. The assessment of significance for the tanezumab SC versus placebo treatment contrasts will use a step-down testing strategy within each of the co-primary efficacy endpoints defined as first testing tanezumab 2.5/5 mg versus placebo, and if statistically significant ($p \leq 0.05$) to then test tanezumab 2.5 mg versus placebo. Finally, a tanezumab treatment group is declared as superior to placebo if the corresponding treatment contrast is significant over all three co-primary endpoints. This testing procedure will maintain the Type I error to 5% or less within each of the co-primary efficacy endpoints, and to less than 5% for all three co-primary efficacy endpoints. An additional (main effects ANCOVA) analysis for each of the co-primary efficacy endpoints will use a per-protocol analysis set, which will exclude subjects who are major protocol deviators.

The primary analysis of the co-primary endpoints will use multiple imputation for missing data, to account for uncertainty around the subject response. The basis for imputing missing values will be dependent on the reasons for missing data. For subjects with missing data due to discontinuation prior to Week 16 for lack of efficacy or for an adverse event or death, imputation will be based on sampling from a normal distribution using a mean value equal to the subject's Baseline efficacy value and the standard deviation (over all treatment groups) of the observed efficacy data at Week 16. For subjects with missing data for any other reason, imputation will be based on sampling from a normal distribution using a mean value of the subject's last observed efficacy value and standard deviation (over all treatment groups) of the observed efficacy data at Week 16. Imputed values for the Patient's Global Assessment of Osteoarthritis will be rounded to integer values from 1 to 5. Imputed values for WOMAC Pain and Physical Function will be truncated at 0 and 10. One hundred imputation samples will be used, and the ANCOVA model described above will be used for each imputation dataset. The final results will be calculated using the combined sets of results from each imputation dataset analysis.

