Number of days of rescue medication use during Weeks 2, 4, 8, 12, and 16	ITT	Negative Binomial Model	BL WOMAC Pain, BL diary average pain, Index Joint (Knee/Hip), Highest KL grade (2, 3 or 4), Treatment Group	LOCF	Secondary Endpoint Analysis
Amount (mg) of rescue medication taken during Weeks 2, 4, 8, 12, and 16	ITT	Negative Binomial Model	BL WOMAC Pain, BL diary average pain, Index Joint (Knee/Hip), Highest KL grade (2, 3 or 4), Treatment Group	LOCF	Secondary Endpoint Analysis
EQ-5D-5L dimensions (Mobility; Self-care; Usual activities; Pain/Discomfort; Anxiety/Depression), EQ-VAS and Overall Health Utility at Baseline and Weeks 8 and 16	ITT	Summary	NA	Observed	Secondary Endpoint Analysis
WPAI endpoints (% work time missed; % impairment while working; % overall work impairment; % activity impairment) at Week 16	ITT	ANCOVA	BL score, BL diary average pain, Index Joint (Knee/Hip), Highest KL grade (2, 3 or 4), Treatment Group (study site as a random effect)	Observed	Secondary Endpoint Analysis
Healthcare Resource Utilization at Baseline, Weeks 24 and 40	ITT	Descriptive Summary	Treatment group	Observed	Secondary Endpoint Analysis
Change from baseline to Weeks 2, 4, 8, 12, 16, 24, and 40 in the NIS score, and Change from Baseline to Worst post-Baseline NIS score	ITT	CMH test	Treatment Group [1]	LOCF (Weeks 2, 4, 8, 12, 16, 24, & 40), Worst post-baseline score	Safety Endpoint Analysis
Survey of Autonomic Symptoms (SAS), number of symptoms and total impact score (by visit and change from Baseline)	ITT	Summary	NA	Observed	Safety Endpoint Analysis

[1] CMH test will be stratified by the levels of the combined stratification parameters (6 levels). If there are <15 subjects in any combined stratification level then the CMH test will be unstratified

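### The CMH sensitivity test for the PGA leaves out baseline PGA, which costs some power and weakens comparison with the planned ANCOVAs

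*SAP*

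**What the plan says.** **Primary analysis (SAP 5.2.2).** The Week 16 PGA change is analysed by ANCOVA "with model terms for Baseline score, Baseline diary average pain, index joint (knee or hip), highest Kellgren-Lawrence grade, and treatment group", with study site as a random effect. On missing data: "The primary analysis of the co-primary endpoints will use multiple imputation for missing data".

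**CMH analysis (SAP 5.2.3).** The change in PGA to each visit up to Week 16 "will also be analyzed using Cochran-Mantel-Haenszel (CMH) test, stratified by the combinations of the two stratification factors". It is run under mixed BOCF/LOCF, BOCF and LOCF. "The mixed BOCF/LOCF analysis at Week 16 will provide a sensitivity analysis for the primary analysis of the PGA". If a stratum has fewer than 15 subjects, the test becomes unstratified. The three PGA CMH rows of Appendix 1 list only treatment group, and their footnote gives the six combined strata and the same fallback. Baseline PGA appears nowhere in this analysis.

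**Other PGA analyses.** Section 3.4.1 requires the corresponding baseline value in the continuous efficacy models (rescue medication excepted). It also requires baseline PGA in models of categorical or binary PGA response. Accordingly, Appendix 1 adjusts for baseline score in the PGA ANCOVAs, both MMRMs and the logistic regression of improvement by at least 2 points.

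**The concern.** The PGA runs from 1 to 5 and improvement is a fall, so baseline limits the possible change: a subject starting at 3 can improve by at most 2 points, one starting at 5 by up to 4. A change score without baseline adjustment pools these subjects as if they had equal room to improve. It also has a larger residual variance than ANCOVA unless the baseline-to-follow-up correlation equals the ratio of the baseline to the follow-up standard deviation.

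Two things are at stake. One is power in a test named as a robustness check for one of three endpoints that must all succeed. The other is comparability. Under BOCF and under LOCF the SAP runs both an ANCOVA and a CMH test on the same imputed PGA data, and those pairs are the natural place to see what the change of method does. When baseline PGA is dropped at the same step, a weaker CMH result is harder to explain.

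**Working it through.** **Inputs from the SAP.** "Approximately 690 subjects (approximately 230 per treatment group) will be randomized to one of 3 treatment groups in a 1:1:1 ratio"; 690/3 = 230. "All tests will be 2-sided", at the 5% level (5.1.1, 5.1.2). The SAP states no PGA standard deviation, correlation, effect size or power, so there is no figure to reproduce.

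**Step 1: variance.** Let sB and sF be the baseline and follow-up SDs and r their correlation.

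- Unadjusted change score: sB² + sF² − 2·r·sB·sF
- ANCOVA: sF²·(1 − r²)

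With sB/sF = 0.6 and r = 0.2: (0.36 + 1 − 0.24)/(1 − 0.04) = 1.12/0.96 = 1.167. The 230 per arm then work like 230/1.167 = 197. With r = 0.6 the ratio is (0.36 + 1 − 0.72)/(1 − 0.36) = 0.64/0.64 = 1, so nothing is lost.

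**Step 2: power.** If ANCOVA has 80% power, the unadjusted change-score test has:

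| sB/sF | r = 0.2 | r = 0.3 | r = 0.5 |
|---|---|---|---|
| 0.6 | 74% | 76% | 80% |
| 0.8 | 67% | 70% | 75% |
| 1.0 | 58% | 62% | 68% |

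The lower rows need baseline PGA to vary nearly as much as Week 16 PGA. SAP 4.2.1 indicates that entry criteria apply to the baseline co-primary scores. That makes a narrow baseline spread, and so the top row, more plausible, though the SAP gives no thresholds.

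**Step 3: simulation on the 5-point scale.** 230 versus 230, six strata, 3,000 runs per setting. Assumed: baselines 3 to 5, baseline SD about 0.62, follow-up SD about 0.97 (ratio about 0.64), a treatment shift of 0.25 before rounding, and a mean-score CMH statistic. Diary pain and site are not simulated, so the comparison isolates baseline PGA.

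| Observed r | CMH as planned | CMH with baseline PGA strata | ANCOVA with baseline PGA |
|---|---|---|---|
| 0.16 | 69% | 77% | 78% |
| 0.29 | 73% | 78% | 79% |
| 0.41 | 80% | 81% | 82% |
| 0.57 | 90% | 90% | 90% |

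With 12% of values (assumed) set back to baseline in both arms, the sequences are 59, 66, 68%; 66, 70, 71%; 74, 74, 76%; and 81, 80, 81%. At zero correlation without that carry-back, outside the range thought relevant, the gap is wider: 62% as planned, 76% with either adjustment. The Monte Carlo standard error at 75% power is √(0.75 × 0.25/3000) = 0.8 points, so one-point differences mean little.

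Two further simulations under somewhat different assumptions showed the same pattern from adding baseline strata: 77 to 84%, 80 to 83% and 85 to 87% at r = 0.12, 0.24 and 0.37; and 70 to 77%, 76 to 80% and 82 to 83% at r = 0.12, 0.24 and 0.36, with no gain at 0.49.

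**Step 4: validity.** The planned CMH test had a simulated type I error of 4.3 to 5.4% in the 3,000-run settings. Across all three simulations both versions stayed within about 4 to 6%.

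**Step 5: what differs between the paired analyses.** Under BOCF and LOCF, ANCOVA and CMH share the imputed data but differ in baseline PGA, diary pain and site. Under mixed BOCF/LOCF no PGA ANCOVA is planned, so that version also differs from the primary analysis in its imputation.

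**The case against.** The strongest reply is that nothing is decided by this test. Section 5.2.2 places the sensitivity analyses outside the testing strategy, and the CMH test is valid as written. Baseline-adjusted checks of Week 16 PGA already exist: ANCOVA in the per-protocol set, ANCOVA under BOCF and LOCF, two MMRMs, and the logistic regression under the same mixed BOCF/LOCF rule. The loss is modest, depends on unstated quantities and can be nil. The calculation also assumes a mean-score statistic, which section 5.2.3 names only for the Neuropathy Impairment Score. All of this stands, and it makes the point a modest improvement.

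A reader might go further and infer that the CMH test exists to check whether PGA steps are equally spaced, and that omitting baseline PGA defeats that purpose. The SAP does not support this. Section 5.2.2 speaks only of a secondary PGA analysis and section 5.2.3 only of a sensitivity analysis. A mean-score CMH on integer changes also treats the steps as equally spaced. The named version changes the imputation and drops diary pain and site as well, so adding baseline PGA alone would not isolate the handling of the scale. Nor do the documents support reading the omission as a bias, or as a threat to the primary PGA conclusion.

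**Conclusion.** The point holds as one of efficiency and comparability. The CMH analysis is the only formal test of the PGA itself that ignores baseline PGA, it departs from the SAP's own covariate practice, and no reason is given. Type I error is about 5%. The power given up is about 0 to 9 points for correlations of 0.1 to 0.6, assuming a baseline SD near 0.6 of the follow-up SD, the simulated effect and a mean-score statistic. It vanishes at the higher correlations. The simpler variance calculation allows up to 80 − 58 = 22 points, but only if baseline PGA is as variable as Week 16 PGA. The BOCF and LOCF CMH results are also less comparable with their ANCOVA counterparts than they need be.

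**What to change.** Either of two changes would do.

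1. **Preferred:** replace or supplement the PGA CMH test with a proportional-odds model of the PGA score. Use baseline PGA, baseline diary average pain, index joint, K-L grade and treatment, under mixed BOCF/LOCF, BOCF and LOCF. The BOCF and LOCF runs then pair closely with the planned ANCOVAs. Site handling still differs, and the mixed version still differs from the primary analysis in imputation, so the result should not be presented as isolating the scale.
2. **Alternative:** keep the CMH test, name its statistic, and add baseline PGA level to the strata. Exempt these finer strata from the under-15 rule. Five baseline levels would give 6 × 5 = 30 cells, averaging 690/30 = 23 subjects. Some would fall below 15, and the rule would then remove all stratification.

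Update section 5.2.3 and the three PGA CMH rows in Appendix 1. No new data are needed and the primary analysis is unchanged. The cost is a proportional-odds assumption in the first case, and some sparse strata that contribute little in the second.

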3.4.1. Covariates

For all models analyzing the continuous primary and secondary efficacy endpoints (except rescue medication) the corresponding Baseline value will be used as a covariate, in addition to Baseline diary average pain. Study site will be fitted as a random effect in the ANCOVA models. The randomization stratification variables of index joint (hip or knee) and highest Kellgren-Lawrence grade (2, 3 or 4) will be included as fixed effects.

A listing of subjects with mis-matches between the stratification variables entered at randomization and the case report form data (including central lab data for Kellgren-Lawrence grade) will be provided. In analysis models, the strata entered at randomization will be used, but for descriptive summarization of the population and identification of subgroups, the strata as indicated on the case report form data will be used.

For the models analyzing the amount and number of days of rescue medication use the model will include terms for Baseline WOMAC Pain, Baseline diary average pain and stratification factors.

The analysis of the incidence of treatment discontinuation due to lack of efficacy will include ... model terms for Baseline WOMAC Pain subscale score, Baseline diary average pain score, index joint, Kellgren-Lawrence grade, and treatment group.

For categorical/binary response endpoints relating to WOMAC Pain and PGA, the corresponding Baseline WOMAC Pain or PGA value will be used as a covariate in the analysis model, in addition to the stratification parameters of index joint and highest Kellgren-Lawrence grade, as well as Baseline diary average pain. For the OMERACT response endpoint, the Baseline WOMAC Pain subscale score and Baseline diary average pain score will be used as covariates in the analysis model, in addition to the stratification parameters of index joint and highest Kellgren-Lawrence grade.

Additional analyses of the three co-primary endpoints will examine the treatment interactions with Study site and Country.

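### The under-15 rule drops all randomisation strata from the CMH tests without any gain in validity; the strata should be kept or pooled (minor)

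*SAP*

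**What the plan says.** SAP section 5.2.3 uses the CMH test for change in the Patient's Global Assessment (PGA) and for change in the Neuropathy Impairment Score (NIS), stratified by the combined randomisation factors. For the PGA it gives the condition for too few subjects as "defined as <15 subjects in any stratification factor". The next paragraph covers every CMH test and gives it as "defined as <15 subjects in any of the 6 combinations of stratification factors". In both cases the consequence is the same: "then an unstratified test will be performed". Footnote [1] of Appendix 1, attached to the PGA and NIS rows, reads: "If there are <15 subjects in any combined stratification level then the CMH test will be unstratified".

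On the role of the PGA test, section 5.2.3 states: "The mixed BOCF/LOCF analysis at Week 16 will provide a sensitivity analysis for the primary analysis of the PGA". For the NIS it adds: "This analysis will be performed for the two treatment comparisons separately".

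Section 2.2 gives the size: "Approximately 690 subjects (approximately 230 per treatment group) will be randomized to one of 3 treatment groups in a 1:1:1 ratio". Section 3.4.1 keeps the strata in the models for continuous efficacy endpoints: "The randomization stratification variables of index joint (hip or knee) and highest Kellgren-Lawrence grade (2, 3 or 4) will be included as fixed effects". The SAP gives no expected share of hip subjects or of any K-L grade, and does not say over which subjects the 15 is counted.

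**The concern.** A CMH statistic adds up within-stratum differences and their variances, and its chi-square approximation rests on the total over strata. A stratum with few subjects contributes little and does no harm. A minimum cell count therefore addresses a problem the test does not have.

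The response is also out of proportion. One sparse cell removes the stratification for every subject, with no pooling step in between. The test then departs from the stratified randomisation and from the primary ANCOVA, which keeps joint and K-L grade. If the PGA sensitivity test differed from the primary result, part of the difference could come from the lost adjustment and not from the categorical method it is meant to examine. At stake are some power and some clarity in a supportive analysis.

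**Working it through.** The SAP states no figure on this point, so there is none to reproduce.

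**Step 1: when the rule fires.** Two joints times three grades gives 6 cells. The smallest expected cell falls below 15 when its share is under 15/690 = 2.2% (all arms) or 15/460 = 3.3% (one active arm plus placebo, 2 × 230).

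**Step 2: chance of firing.** The shares below are assumptions. Joint and grade are taken as independent, with K-L 4 at 30%. For one cell, P(count < 15) is the binomial probability with N subjects and p = joint share × grade share. For hip 10% and K-L 2 20%, the two cells that matter are hip by K-L 2 (p = 0.02) and hip by K-L 4 (p = 0.03):

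- N = 690: 0.592 and 0.077, so at least one is about 1 − (0.408 × 0.923) = 0.62.
- N = 460: 0.953 and 0.592, so at least one is about 1 − (0.047 × 0.408) = 0.98.

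The product treats the two counts as independent; a multinomial simulation of all six cells gave the same values to two figures.

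| Assumed hip / K-L 2 | Any cell < 15, N = 690 | Any cell < 15, N = 460 |
|---|---|---|
| 10% / 20% | 62% | 98% |
| 15% / 20% | 8% | 62% |
| 20% / 10% | 59% | 95% |
| 30% / 30% | about 0 | about 0 |

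If the loose parenthesis were read literally, as a single factor level, a level with 10% of subjects would hold 69 of 690 or 46 of 460, and the chance of fewer than 15 is about 0.

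**Step 3: does a small cell harm the stratified test?** With g indexing strata, y the change score, n1 and n0 the arm sizes and n = n1 + n0, the one-degree-of-freedom statistic is

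Q = [Σg (sum of treated y − n1·ȳg)]² / Σg [n1·n0 / (n(n − 1)) · Σ(y − ȳg)²].

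It was simulated 10,000 times with 460 subjects, hip 15%, and K-L 2/3/4 at 12%/45%/43%. The smallest cell is 0.15 × 0.12 × 460 = 8.3, rounded to 8. Scores were rounded normal values with SD 1 before rounding, and randomisation was balanced within strata. The stratum effects and the 0.27 SD treatment shift are assumed.

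| Stratum effect per grade | Type I error, stratified | Type I error, unstratified | Power, stratified | Power, unstratified |
|---|---|---|---|---|
| 0 SD | 0.050 | 0.050 | 0.793 | 0.793 |
| 0.3 SD | 0.053 | 0.049 | 0.791 | 0.781 |
| 0.6 SD | 0.048 | 0.034 | 0.794 | 0.749 |

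The simulation standard error near 0.05 is √(0.05 × 0.95 / 10,000) = 0.002, so the stratified values are consistent with 5%. The power loss is 0.0, 1.0 and 4.4 points. A separate run (6,000 trials, smallest cells of 7 to 10, stratum shifts of 0.2 to 0.4 PGA points) agreed: 5.0% to 5.4% stratified, 4.0% to 5.1% unstratified, and 1 to 4 points of power lost.

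**The case against.** The strongest reply is that nothing confirmatory depends on this. The fallback is fixed in advance and looks at stratum counts, not outcomes, so it leaves no room to choose a favourable result. The co-primary ANCOVA and the key secondary logistic regression keep both factors. The PGA CMH is one of several checks on that endpoint, and the per-protocol, BOCF, LOCF and MMRM analyses all retain the strata. All of this stands, and it keeps the point minor.

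Four stronger readings are tempting and are not supported:

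- **That the unstratified test is invalid.** It is valid here: neutral to conservative, with no inflation of type I error.
- **That the rule is likely to fire.** The SAP gives no joint or K-L shares. Over the assumed range the chance runs from about 0 to 98%, and counting over 690 instead of 460 subjects can move it from 62% to 8%.
- **That section 5.2.3 holds two rival triggers.** The PGA sentence itself speaks of combination groups, and both the general rule that follows and the Appendix 1 footnote use the six combinations. Only the parenthesis is loose, and the intended reading can be recovered.
- **That the NIS test loses the same power.** Nothing was computed for the NIS, and the SAP does not indicate that joint or K-L grade predicts NIS change.

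**Conclusion.** The point holds as a minor one. The fallback gives no validity benefit, because CMH needs no minimum stratum size. When the strata are prognostic, it makes the PGA sensitivity test somewhat conservative and costs up to about 4 points of power; when they are not, it costs nothing. A similar effect on the NIS test is possible but not quantified. These sizes rest on assumed stratum shares, stratum effects and treatment shift, with the largest loss at an assumed 0.6 SD per grade. The trial's primary and key secondary conclusions do not depend on the rule. The counting base for the 15 is a real gap as long as a threshold is kept.

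**What to change.** Delete the under-15 rule from both sentences of section 5.2.3 and from Appendix 1 footnote [1], and always stratify the CMH tests by the six combinations. If a safeguard is wanted, state in advance that adjacent K-L grades are pooled within joint, so that one sparse cell does not remove all strata. If any threshold stays, define it on the six combinations in all three places, correct the parenthesis that refers to a single factor, and say whether it is counted over all randomised arms or within each comparison with placebo. The cost is SAP wording and a small programming change, with no extra data and no effect on the primary or key secondary analyses.
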